I. Research Project Title, Purpose, Anticipated Project Duration and Inclusion of Proprietary Information

Protocol Version: May 8 2017

Investigators: [name], [name], [name]

Title:

Remote monitoring of symptoms and cognitive function using Telehealth: *T- Liver* project

Purpose:

End-Stage Liver Disease (**ESLD**) is one of the ten leading causes of death in US. It is marked by episodic acute exacerbations of the underlying liver disease which often leads to severe symptoms, poor quality of life, mental deterioration and repeated hospitalizations. The **overall purpose** of this project is to introduce a telehealth based intervention (involving remote monitoring of symptoms and cognitive function assessment) initiated during the time of hospital admission of ESLD patients. This will support enhanced clinical care and improve self-management in ESLD population. In addition, it will reduce healthcare utilization, improve medication adherence and overall health outcomes.

II. Research Project Overview

The **primary goal** is to develop and implement a systematic clinical approach for remote monitoring of symptoms and cognitive function in ESLD patients, through developing a telehealth based intervention. The intervention includes assembling specific apps on an ipad/smartphone/tablet through a web based secured system, having patients respond to periodic assessments and transmission of results instantly to providers, who will follow specified clinical pathways stratified by severity scores.

Methods: This is a single arm study to assess the effectiveness of an experimental telehealth intervention within the treatment of ESLD, and compare it with a historic cohort. All inpatients with advanced liver disease and at least 1 complication will be eligible to participate. The study group receives the Telehealth intervention and will be given an ipad/smartphone preloaded with the instruments used for symptom monitoring and cognitive function assessment during the hospital admission. A research coordinator will consent the patients and conduct a 30-minute introduction to use of device on the day of enrollment (within 24-48 hours of admission). The second assessment will be done on day 2, and third assessment on day of discharge. After that, the patient will be told to do the study assessments daily at home. The study assessment results will be reviewed by the providers on the same day, and based on the severity scores clinical actions will be taken and documented.

IV. Expected Research Outcomes and Benefits -
--

Primary Outcomes:

- 1) Healthcare utilization (30 and 90-day readmission)
- 2) Changes in severity scores of symptoms and quality of life over time.

3) Patient experience/satisfaction.

Benefits of the research: Applying telehealth intervention (inclusive of remote monitoring of symptoms and cognitive function) with a well-defined clinical algorithm at the time of discharge of patients with ESLD, who are prone to impaired quality of life, adds a **new dimension** to the care delivery model. This new post-hospital discharge algorithm is expected to have positive effects on many parameters, including readmission rates, patient satisfaction, and above all on the health outcomes. Arguably, these improvements will reduce health care costs among a group of patients with ESLD, who are high utilizers of healthcare services. Benefits to individual patients include monitoring of their own symptoms, and cognitive function, which will allow early detection of hepatic encephalopathy and/or other complications.

VII. Evaluation Component and Research Evaluative Procedures - Oversight and Statistical Tests

Oversight: The PI will be overseeing the implementation of the project along with the Co-Investigator. Since the study involves patients who are admitted to the hospital, and offers them a device to improve their own care, the likelihood of participation is high. We will assess the attrition rates and other technical issues during the project. Higher rates of no response to timed assessments from enrolled patients will trigger an alert to the research coordinator, who will then call the patients to make sure device is working appropriately and explore the reasons for missing responses. Furthermore, a detailed discussion at the time of enrollment about the project and expected responsibilities from patients will reduce the missing data points.

Statistical Tests: The data for study group will be described using both graphic and summary statistics. Process data on participation, usage and satisfaction with telehealth intervention will be collected and summarized to assess intervention fidelity. We will assess the change in percent readmissions at 30 days and 90 days in the study group from baseline to 3 months. The average rate of change in the defined outcomes in longitudinal (overtime) analyses using paired t tests and 95% CIs of the differences in the two groups will be conducted. The trajectories of symptom and quality of life scores will be illustrated by graphing individual patient values over time course of the study for the intervention group. We will test whether the relationship between study outcome and study arm differ with the severity of disease as assessed by MELD (Model for End Stage Liver Disease) score using two-way analysis of variance for repeated measures.

(B) Performance Measures

B) Performance measures:

- 1) Number of patients enrolled in the study.
- 2) Completion of 7, 28 days and 3 months assessment of symptoms and cognitive function by the patients.

- 3) Attrition rates of enrolled patients.
- 4) Efficiency of the technical device provided to patients as assessed from ease of use by patients and providers.
- 5) Scholarly activities (publications and presentations) resulting from study data.

VIII. Health Disparities

This project will target the patient population at Einstein, which is largely underserved, and minority. No racial/ethnic or gender group will be excluded from the proposed study. Furthermore as the study involves providing an ipad/smartphone to patients, it eliminates any existing disparity of access for anyone who participates.

XI. Research Plan

(1) Specific Aims

The **specific aims** are:

1. To develop and implement a systematic clinical approach for remote monitoring of symptoms and cognitive function in ESLD patients, through assembling specific apps on an ipad/smartphone using web based cloud technology (referred to as telehealth intervention).
2. To evaluate the impact of our telehealth intervention on health care utilization (30/90 day readmissions)
3. To assess prospectively the comparative efficacy of telehealth intervention within the treatment of ESLD, in improving i) symptom scores, ii) patient reported quality of life, and iii) satisfaction with device and questionnaire. We hypothesize that Telehealth intervention will show improvement in these domains over time [a 10% improvement in scores from baseline to 3 months will be considered clinically significant]

(2) Background and Significance

End-Stage Liver Disease (**ESLD**) is one of the ten leading causes of death in US.ⁱ Hospitalization rates due to ESLD and its complications have skyrocketed by 93% (due to *hepatorenal syndrome*), 62% (due to *portal hypertension*), and 190% due to Hepatitis C and its complications from 2004-05 to 2010-11.ⁱⁱ Developing interventions which can potentially reduce readmissions and healthcare utilization are a national priority according to the Affordable Care Act.ⁱⁱⁱ **Telehealth** offers a unique platform to remotely monitor individual patients and offer enhanced care at the time of need, and has shown success in congestive heart failure, lung disease and diabetes.^{iv} There is no research demonstrating its utilization or efficacy for liver disease patients. Hence, we propose to develop and test the effectiveness of a ***T-Liver intervention*** to remotely monitor the symptoms (pain, shortness of breath) weight, temperature, and cognitive function (using symptom questions and a stroop test) to reduce healthcare utilization, improve patient satisfaction and health outcomes.

“HGE healthcare solutions” is a group of experts who have pioneered some work in telehealth, and created a smartphone based COPD app (Chronic Obstructive Pulmonary Disease), which assesses daily symptoms and triggers alerts to providers for immediate treatments. This app has shown to improve health outcomes and reduce hospitalizations by changing the approach of health care to proactive than reactive. ^{v vi} We will be partnering with this company in creating and delivering our telehealth intervention. The company operates on a HIPAA secured platform, which maintains confidentiality and security of the data. They also offer technical assistance to end users during normal business hours.

(3) Research Design, Methods and Activities -
--

Methods: This is a single arm trial to assess the effectiveness of an experimental telehealth intervention within the treatment of ESLD, and compare it with a historic control. The study patients continue to receive the routine standard of care, which may involve addressing symptoms based on individual needs and circumstances. All participants will be given an ipad/smartphone preloaded with the instruments used for symptom monitoring and cognitive function assessment. A research coordinator will consent the patients and conduct a 30-minute introduction to use of device on the day of enrollment. Repeat assessments will be done as shown in **Table 1** above. All patients will receive the standard of care discharge planning, including discharge instructions and a confirmed follow-up ambulatory visit within 2-4 weeks.

Inclusion Criteria: All patients being discharged from the inpatient liver practice of the Einstein Healthcare Network (EHN) who meet the following criteria will be eligible.

- ✓ Patients must be age 18 years or older
- ✓ Ability to provide informed consent, and must be able to cognitively answer questionnaires
- ✓ Patients who received a diagnosis of Advanced Liver Disease with at least 1 of the complications (Hepatorenal Syndrome, Portal Hypertension, Ascites, Hepatic Encephalopathy)
- ✓ Patient must be able to read/ speak English
- ✓ Patient must have a support person

Exclusion Criteria:

- ✓ Cognitive impairment which precludes participation
- ✓ Projected survival, in the opinion of the provider, of less than six months
- ✓ Current psychosis or confusion, precluding a patient from being consented
- ✓ Patients being discharged to nursing homes
- ✓ Patients with red green color blindness (as they will not be able to respond to stroop test questions).

Telehealth Intervention:

Patients will receive a 30-minute introduction to the use of ipad/smartphone, and instructions to respond to the following assessments. Initial assessments will be performed on the day of enrollment, and all of them will be repeated periodically (**Table 1**), for a total of 3 months study

participation. The assessments include the following: Pain (severity, location), shortness of breath (at rest or with mild activity), cognitive function assessment (drowsy, hard time concentrating, irritable, trouble remembering things, slurred speech, unsteady gait), and stroop test (color matching test, one cycle lasts 45 seconds).

Weight monitoring: Monitoring weight will allow assessment of fluid retention in ESLD patients, and help detect any development/ worsening of ascites. Patients will be instructed to enter their daily weights for the first month, and then every week for next 2 months. Any weight gain of more than 2 lbs within 1-2 days for 3 consecutive days will trigger a phone call by the providers.

A simplified step by step guide summarizing the instructions will be included with the device. Patients will be given a toll-free number that will be available during work hours (9am to 5pm) for any technical issues, and will be urged to complete assessments by 11 am on a daily basis.

Site: Levy 7 is the home of the “Liver Care Center at Einstein”, a 15 bed inpatient unit dedicated to the care of patients with liver disease. This inpatient unit is the site of identification and recruitment of patients in this project.

Recruitment methods: The research coordinator will contact eligible patients within 24-48 hours of admission and conduct informed consent. All patients who consent will be then randomized to either of the 2 groups. We assume 3-4 patients will be enrolled per week, for 7 months of enrollment period.

Sample size and power: Assuming a baseline risk of readmission in the historic control of 40% and 10% attrition rates, a sample size of 50 patients will be sufficient to detect a difference of 35% or greater in the intervention group. Accepting a type I error rate of no more than .05, and a Type II error rate of .20, we will have 80% statistical power to detect a difference of this magnitude or larger.

Retention strategies: Patients will be informed about the purpose of the study and their responsibilities at the time of consent by the research coordinator. All patients with a support person will be eligible. Strategies (i.e. education about value of study participation) will be added if recruitment rates fall within 20% of target.

Analysis plan: Medical records will be utilized to capture the disease severity, diagnosis, duration of liver disease and presence of comorbidities. Patients enrolled into the study will be followed up for 6 months. Descriptive and analytics statistics will be done using linear correlation and regression. We will compare the clinical markers at baseline with 3 month value using unpaired t test.. .

Limitations:

Patient Attrition: this is an anticipated problem, as physical and cognitive deterioration may make the completion of questionnaires difficult. This limitation will be minimized by the short interval assessments and completion of study at 3 months.

(4) Protection of Human Subjects -

- (a) **Risks to subjects:** There is no medical risk to any participant and no sharing of protected health information in this project. It is completely up to the participants to agree for this study. Refusal for participation will not impact their health care in the office. There are minimal risks to participants related to their completion of survey questionnaires. There may be some emotional distress as they complete the symptom and quality of life questions, but this will influence and enhance their own care. Patients may have technical difficulties, which will be addressed through availability of a help desk and the research coordinator during work hours.
- (b) **Adequacy of protection against risks:** There are no known risks in this study. All study personnel have completed the IRB required CITI training, and will be trained appropriately. Confidentiality is maintained through Einstein's secured system and the secure administration through HGE. The PI and Co-Investigator will be available to answer any of the patient's concerns. The research coordinator will conduct an in-depth informed consent explaining the purpose of the project, and the expectations from patients to respond to the assessments in a timely way. All the information collected is through a secured password protected system, which allows encrypted data transmission to the providers
- (c) **Recruitment of subjects:** All patients discharged from the Inpatient liver unit who meet the eligibility criteria will be approached for consent. Once the patients agree to participate, the details of the study and device operations will be discussed. If the patient needs more time to decide, we will allow them to take the information home and get back to the research coordinator within 1-2 days.
- (d) **Informed consent:** An in-depth informed consent will be conducted in person using paper version. The IRB approval will be attached.
- (e) **Data confidentiality** and provision of medical or professional intervention, if needed: Einstein Healthcare Network's Human Research Protection Program (HRPP) is a comprehensive system to ensure the protection of the rights and welfare of subjects in Human Research. It is comprised of the EHN leadership, Office of Research and Technology Development (ORTD), Institutional Review Board (IRB), investigators and their study staff and relevant departments and units. The HRPP not only promotes compliance with relevant laws, regulations and professional and ethical standards at all levels, it addresses the needs and concerns of researchers and enhances support of their endeavors. The HGE has a secured system through which the patients will

complete the study assessments and communicate with providers. All data collected will be completely confidential, and will not be shared with anyone outside of this project.

- (f) **Potential benefits** of the research to subjects: Since this study involves close monitoring of symptoms and development of any hepatic encephalopathy, it will enhance patient centered care through timely management of symptoms, and early detection of complications of ESLD.
- (g) **Importance of knowledge to be gained:** The knowledge gained from this project will enable the use of technology in care of liver disease patients in a meaningful way, and allow early detection of symptoms/ problems which will trigger clinical actions as needed and thereby make the approach to care more proactive than reactive. This will potentially engage patients in their own care, and improve the healthcare service delivery model for ESLD.
- (h) Inclusion of women, children and minorities in the research: All eligible candidates more than 18 years of age are included in this study, irrespective of any specific race / sex, etc.

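### 30/90-day readmission, the first-listed primary outcome, has no clearly specified, suitable test against the historic cohort on which the study is designed and sized

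*Combined protocol and SAP*

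**What the plan says.** - **Outcome.** Section IV lists first among the primary outcomes "Healthcare utilization (30 and 90-day readmission". Specific Aim 2 in section XI(1) is about the same outcome.
- **Design.** The Methods paragraph in section II describes a single-arm study that will assess the intervention "and compare it with a historic cohort". Section XI(3), Methods, repeats this: "and compare it with a historic control".
- **Sizing.** Section XI(3), Sample size and power, begins "Assuming a baseline risk of readmission in the historic control of 40" (per cent). It goes on to 10% attrition, 50 patients, a difference of 35%, type I error .05 and power 80%. It does not say whether the 40% is a 30-day or a 90-day risk.
- **Analysis of readmission.** Section VII, Statistical Tests: "We will assess the change in percent readmissions at 30 days and 90 days in the study group from baseline to 3 months".
- **Next sentence.** It covers the defined outcomes over time, "using paired t tests and 95% CIs of the differences in the two groups will be conducted".
- **Severity of disease.** The same section will test "whether the relationship between study outcome and study arm differ with the severity of disease", by two-way repeated-measures analysis of variance with MELD.
- **Analysis plan, section XI(3).** It adds linear correlation and regression without naming an outcome, and an unpaired t test of clinical markers at baseline against 3 months.
- **Recruitment methods, section XI(3).** "All patients who consent will be then randomized to either of the 2 groups".

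**The concern.** The comparison that the design and sample size call for is a yes/no outcome in study patients against the same outcome in different, earlier patients. The analysis text does not supply it.

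The readmission sentence describes a change within the study group. No pre-enrolment readmission measure is defined from which a change could be taken. The Data Safety Monitoring Plan takes medical history from the records at baseline but does not make prior readmission a measure.

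A paired t test needs two linked measurements on the same patient. Study and historic patients are not linked, and readmission is binary.

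The randomisation sentence contradicts the single-arm design, so a reader cannot tell whether the second group is historic or concurrent.

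At stake is control of the type I error that the plan caps at .05. If the test, the comparator's form (fixed rate or observed cohort) and the primary window are all open, they can be settled after the readmission counts are known.

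**Working it through.** **1. The plan's own figure.** Inputs from Sample size and power: 40% control risk, difference 35 (read as percentage points, so 40% v 5%), two-sided .05 (sidedness assumed), power .80, attrition 10%. For two independent proportions with pooled variance and mean rate .225:

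n per group = [1.960 × √(2 × .225 × .775) + 0.842 × √(.40 × .60 + .05 × .95)]² / .35² = 21.1, so 22.

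22 / 0.9 = 24.4, so 25 per group, 50 in total.

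The stated 50 is thus consistent with an unpaired comparison of two proportions, a method the analysis sections never name. With 35% read as relative (40% v 26%) the same formula gives 176 per group, so 50 is not reproduced.

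**2. Candidate analyses in the text.**

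| Text | Names readmission | Compares with historic patients | Suits a binary outcome in unpaired groups |
|---|---|---|---|
| Section VII, change from baseline | yes | not stated | no test named |
| Section VII, paired t tests and CIs | only through the defined outcomes | perhaps, through the two groups | the named test does not |
| Section VII, MELD ANOVA | no | perhaps, through study arm | no; it tests effect modification |
| Section XI(3), linear regression | no | no | not assigned |
| Section XI(3), unpaired t test | no (clinical markers) | no | no |

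No chi-square, Fisher, binomial, logistic or time-to-event analysis of readmission appears anywhere.

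**3. A boundary illustration.** Evaluable patients: 50 × 0.9 = 45, assuming that dropouts also lose readmission data. Take 11/45 = 24.4% (Clopper-Pearson 95% CI 12.9% to 39.5%). This result was picked because it is the largest count at which the exact test against 40% shows a significant reduction.

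- Exact test against a fixed 40%: P(X ≤ 11 | 45, .40) = .0216; doubled, P = .043. The minimum-likelihood version gives .034. At 12/45 the doubled value is 2 × .0446 = .089.
- Pearson chi-square, no continuity correction, against 40% observed in N historic patients. N is assumed, because the documents give none. For N = 100: pooled rate 51/145 = .352; z² = (.1556)² / [.352 × .648 × (1/45 + 1/100)] = 3.29; P = .070.

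| Historic patients (assumed) | 50 | 100 | 200 | 500 |
|---|---|---|---|---|
| Chi-square P for 11/45 | .106 | .070 | .051 | .040 |
| Actual two-sided error, estimated 40% treated as fixed | 12.2% | 8.0% | 5.7% | 4.4% |
| Actual two-sided error, chi-square | 4.8% | 5.0% | 5.0% | 5.0% |

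The second row is the sum over y of Bin(y; N, .40) × P(exact test of p = y/N rejects | n = 45, p = .40). If 40% were truly fixed, the exact test's size would be .0216 + .0120 = .0336 (rejecting at 11 or fewer, or 26 or more).

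**4. How wide the boundary is.** With the historic rate held at exactly 40%, the two tests disagree only at 10, 11, 26 or 27 readmissions for N = 50, only at 11 for N = 100 or 200, and only at 25 for N = 500. At 9/45 or fewer both reject for all four sizes. If the true rate is 5%, the chance of landing on a disagreement is about .0001 or less. If it is 26%, the chance is .25, .13, .13 and about 0 for the four sizes.

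**The case against.** The strongest reply is that the plan does promise a comparison. The sentence with the paired t tests can be read as two items: paired tests for change over time, and 95% CIs for between-group differences in the defined outcomes, readmission included. The sample-size paragraph uses baseline risk for the historic rate, so a change from baseline might loosely mean study group against historic rate. Both readings are possible. For that reason a reader who infers that no between-group comparison is planned at all goes further than the text allows. What remains is that neither reading yields a method for the interval, a suitable test or an identified comparator.

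Second, 11/45 is a boundary result. That is correct. A reader might infer that the choice of test will generally decide the trial, and step 4 does not support this: under the 5% rate that reproduces the sample size the choice is almost immaterial. It matters for a more modest effect.

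Third, naming a test does not remove every choice. The exact test depends on its two-sided convention: 13/50 gives P = .056 by doubling and .044 by minimum likelihood. Against 200/500, 11/45 gives .040 by Pearson and .054 by Fisher. This stands, and it argues for stating the convention in advance rather than for any one test.

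Fourth, section II gives the primary goal as developing and implementing the monitoring approach. That tempers the point only modestly, since readmission heads the primary outcomes and drives the sample size.

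Finally, a reader might take the match of 50 to two groups of 25, with the randomisation sentence, as proof that a concurrent control was intended. The documents show no sample-size formula and describe the study as single arm twice, so the match shows only consistency.

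**Conclusion.** The point holds as an under-specified and partly mismatched analysis of the first-listed primary outcome. It is more than missing detail, because the one test that could be taken to apply does not fit the comparison on which the study is sized.

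The consequence is an open choice that can move a borderline result across .05. It can also raise the actual error to between 5.7% and 12.2% if a rate estimated from 200 down to 50 patients is treated as known. With 500 historic patients the problem largely disappears (4.4%).

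These sizes rest on 45 evaluable patients, a true common rate of 40%, two-sided testing and assumed cohort sizes. The absence of a suitable named test rests on none of them.

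**What to change.** Replace the readmission sentence in section VII with text such as:

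> The proportions readmitted within 30 and within 90 days of index discharge will be compared with the historic cohort by risk difference with 95% CI and a prespecified two-sided 5% test for two independent proportions (for example Pearson chi-square). If only a fixed historic rate is available, an exact one-sample binomial test (two-sided P = twice the smaller tail) with Clopper-Pearson 95% CI will be used, and the report will state that this ignores uncertainty in the historic rate.

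In addition:
- State the historic numerator and denominator for each window, and which window is primary.
- Limit paired t tests to within-patient change in repeated scores.
- Reconcile the randomisation sentence in Recruitment methods, and the references to two groups and study arm in section VII, with the single-arm design.

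The cost is a text change plus historic counts for each window. If only a fixed rate exists, the fallback needs no extra data, but its limitation must be reported. A rule for deaths before readmission, restricting the historic cohort by eligibility, and a MELD-adjusted model are optional additions and not part of this defect. The last two would need chart abstraction for the historic patients.

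### Change in symptom scores is a primary outcome asked for daily, yet the main analysis is a paired t test that leaves the intermediate scores out and is probably less precise than the data allow

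*Combined protocol and SAP*

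**What the plan says.** Section IV lists change over time in symptom severity and quality-of-life scores as the second primary outcome. For its analysis, Section VII (Statistical Tests) offers "The average rate of change in the defined outcomes in longitudinal (overtime) analyses using paired t tests", with confidence intervals. That sentence does not say which two occasions are paired. The best clue is the hypothesis in Section XI(1), where "a 10% improvement in scores from baseline to 3 months will be considered clinically significant". The Analysis plan in Section XI(3) also sets baseline against the 3-month value, though for clinical markers and with an unpaired test.

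On how often scores are collected, the document gives more than one account:

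- Section II, Methods, after the enrolment, day 2 and discharge assessments: "After that, the patient will be told to do the study assessments daily at home".
- Section XI(3), Telehealth Intervention: patients "will be urged to complete assessments by 11 am on a daily basis".
- The same section: "Initial assessments will be performed on the day of enrollment, and all of them will be repeated periodically", with reference to a Table 1 that is not in the text available for this review.
- Section VII(B), Performance Measures: "Completion of 7, 28 days and 3 months assessment of symptoms and cognitive function by the patients".
- Weight has its own schedule: "Patients will be instructed to enter their daily weights for the first month, and then every week for next 2 months".

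Three other analyses could touch the repeated scores. Section VII plans graphs of individual trajectories and a repeated-measures analysis of variance for whether results differ by MELD score. Section XI(3) adds "Descriptive and analytics statistics will be done using linear correlation and regression", with no outcome, time term or patient effect given.

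**The concern.** The sentence announces a longitudinal analysis but names a test that takes one difference per patient. If that difference is enrolment day against one day at 3 months, each end carries the full day-to-day noise of a single answer, and everything recorded in between is left out of the main estimate. A good or bad day at either end can hide a real change or suggest one that is not there. This would hold even if nobody dropped out.

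A single target day is also fragile. A patient who skips that day has no 3-month value, however many entries surround it. Section VII expects missing responses and plans calls to chase them.

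None of the other analyses fills the gap. The graphs estimate nothing, and the analysis of variance is reserved for the MELD question. The regression is unspecified; if it were run on daily rows without a patient effect, it would treat one patient's days as independent and misstate the standard errors.

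**Working it through.** The plan gives no precision or sample-size figure for symptom scores, so there is none to reproduce. The stated 50 patients concern readmission.

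**Share of entries outside a two-point comparison**, 1 − 2/(entries per patient):

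| Schedule | Entries | Unused |
|---|---|---|
| Daily for 90 days | 90 | 1 − 2/90 = 97.8% |
| Weight: daily for 30 days, then about 9 weekly entries | 39 | 1 − 2/39 = 95% |
| Baseline, day 7, day 28, 3 months | 4 | 1 − 2/4 = 50% |
| The same plus day 2 and discharge | 6 | 1 − 2/6 = 67% |

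**Precision.** The documents give no SD, within-patient correlation or variance of change. Everything below is therefore assumed: total SD 1; stable between-patient share of variance 0.3 to 0.8, so daily-noise variance e = 0.7 to 0.2; variance of true change d = 0.1 to 0.3; first-order autoregressive daily noise with lag-1 correlation ρ.

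- Two single days: Var(change) = d + 2e.
- Single enrolment day against the mean of the last 7 days: Var(change) = d + e + e·f, where f is the sum of the 7 × 7 noise correlations divided by 49. This gives f = 0.143 at ρ = 0, 0.348 at 0.5, 0.798 at 0.9 and 0.893 at 0.95.

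The extreme cases:

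| ρ | e | d | Two days | End window | SE ratio | Cut in SE |
|---|---|---|---|---|---|---|
| 0 | 0.7 | 0.1 | 1.500 | 0.900 | 0.77 | 23% |
| 0.5 | 0.2 | 0.3 | 0.700 | 0.570 | 0.90 | 10% |
| 0.9 | 0.7 | 0.1 | 1.500 | 1.358 | 0.95 | 5% |
| 0.95 | 0.2 | 0.3 | 0.700 | 0.679 | 0.98 | about 2% |

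The gain is thus 10% to 23% for ρ from 0 to 0.5 (equivalent to 1/0.90² to 1/0.77², about 1.2 to 1.7 times the patients), and 2% to 5% for ρ of 0.9 to 0.95. Only the 3-month end is averaged, because the baseline is an enrolment-day assessment and no 7-day baseline window exists.

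**A straight-line slope instead.** With the same variances, an ordinary least-squares slope over 91 daily values, scaled to 90 days, has SE ratios against two single days of 0.36 to 0.73 for ρ of 0 to 0.5 and 0.93 to 0.96 at 0.9. At 0.95 it is 1.05 to 1.07, which is worse than two points. It can also be biased. If recovery after admission is exponential with an assumed time constant of 7 to 21 days, slope × 90 recovers only about 41% to 79% of the day-0-to-90 change.

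**Missing target day.** With an assumed 70% daily adherence, a single day is missing for 30% of patients. If days are missed independently, a 7-day window has at least one entry with probability 1 − 0.3⁷ = 99.98%. Missed days that cluster would lower this.

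**The case against.** A paired comparison of baseline with 3 months answers the hypothesis in Section XI(1), which is framed as that contrast and not as a slope. A reader might infer that a paired t test estimates no rate at all. That goes too far: mean change over a fixed 3 months, divided by 3, is an average rate in a simple sense. What it omits is the course between the ends.

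The two single days are also inferred. Paired tests, in the plural, could be run at several occasions or on averaged values, and the sentence excludes neither. Part of the fault is under-specification. This stands, but it does not help the plan: no estimator using the repeated scores is written down for the main change.

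A reader might take 98% as the share of data thrown away. It is correct only for daily entry throughout, and Section VII(B) supports a much sparser schedule. Quality of life is not in the Section XI(3) list of device assessments, so its frequency is unknown. Nor are the intermediate scores wholly discarded, since they feed the graphs and may feed the MELD analysis.

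Finally, a reader might conclude that the result is needlessly imprecise. The documents cannot show that. Section I describes episodic exacerbations, which may persist for days, and strong autocorrelation would remove most of the gain. A separate calculation with a generalised least-squares slope, under wider assumptions, gave SE ratios from 0.25 to about 1.00, so the loss could be large or negligible.

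**Conclusion.** The point holds in a limited form. For a primary outcome asked for daily, the plan's named test most naturally uses two occasions per patient. At least half of the repeated scores then stay out of the main estimate on any schedule the document describes, and about 98% do so under daily entry for 90 days. Precision is probably lower than the data allow. The end-window gain is 10% to 23% of the standard error with weak to moderate serial correlation and 2% to 5% with strong correlation, all on assumed variances. Protection against a missing single-day entry is a further benefit and does not depend on those variances. The change is worth making because it costs so little, not because a large loss has been demonstrated.

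**What to change.** Replace the paired t test sentence in Section VII with wording such as:

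> Change from the enrolment baseline to 3 months will be estimated with a mixed model for repeated measures on all available scores (enrolment, day 2, discharge and home entries), with patient random effects, serially correlated residuals and a flexible time effect (for example, weekly categories), reported as the change at 3 months with 95% CI. A simple paired comparison will use the mean of the last 7 daily entries before 3 months against the enrolment value.

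Keep enrolment as its own time level, so that the in-hospital baseline of the Section XI(1) hypothesis is not lost. Do not impose a straight line. State one assessment schedule for each score, including quality of life. Run any correlation or regression on daily rows only with a patient effect.

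The cost is analysis-plan wording and slightly more analysis work, with no new data and no added patient burden. The downside is that the precision gain will be small if daily scores prove strongly autocorrelated.
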